9.3.2.1.17 Eclampsia

The convulsive manifestation of the hypertensive disorders of pregnancy and is among the more severe manifestations of the disease. Eclampsia is defined by new-onset tonic-clonic, focal, or multifocal seizures in the absence of other causative conditions, such as epilepsy, cerebral arterial ischemia and infarction, intracranial hemorrhage, or drug use ([\[ACOG\] American College of Obstetricians and Gynecologists 2020](#), [\[WHO\] World Health Organization 2011](#)).

9.3.2.1.18 Preterm Prelabor Rupture of Membrane:

Membrane rupture before labor that occurs before 37 weeks of gestation ([\[ACOG\] American College of Obstetricians and Gynecologists 2020](#), [\[WHO\] World Health Organization 2015](#)).

9.3.2.1.19 Maternal Death

Maternal death is defined as the death of a pregnant woman during pregnancy, labor, or delivery. Maternal deaths for up to 12 weeks after delivery will also be reported.

9.3.2.1.20 Any Adverse Events during Pregnancy

Includes all variables from Section [9.3.1.3.1](#).

9.3.2.1.21 Any Adverse Events Experienced by the Infant

Includes all variables from Section [9.3.1.3.1](#) from birth up the first year of life.

9.3.2.1.22 Any adverse events for lactating females and infants through breastfeeding

Includes all variables from Section [9.3.1.3.1](#).

9.3.3 Baseline and Follow-up Variables

The following baseline and follow-up variables will be collected at enrollment for all participants with PNH and during pregnancy and infant birth:

- Participant characteristics and demographics: Date of birth or age in years (where allowed), sex, race/ethnicity (where allowed), country of residence
- Vaccination: for meningococcal (group C, AC, ACWY, and B), Hemophilus influenzae type b, pneumococcal, COVID and other. Dates of vaccinations and vaccination brands where possible
- Clinical history relevant for PNH, including previous PNH treatment and date of last administration
- Any concomitant medication
- Breastfeeding:
 - Yes/No
 - Duration of breastfeeding (in weeks or months during the first year of age of the infant)
 - Exclusively breastfeeding (Yes/No)
 - Supplementing with formula (Yes/No)
 - The ages of infants when formula supplementation began
 - Reasons for any cessation of breastfeeding
- Potential confounding factors affecting safety, pregnancy, and infant outcomes
 - Maternal medical history (e.g., hypertension, diabetes, seizure disorder, autoimmune disease, known risk factors for adverse pregnancy outcomes including environmental or occupational exposures)
 - Obstetric history: Number of pregnancies and outcome of each (live birth, miscarriage, pregnancy termination [elective or therapeutic], ectopic pregnancy), previous maternal pregnancy complications, previous fetal/neonatal abnormalities and type
 - Family history (specify type, maternal or paternal, among others): Malformations, genetic disorders, multiple fetuses/births

Participant data will be collected in the Crovalimab Silo by the clinician and/or qualified designee in accordance with routine clinical practice according to [Table 1](#).

Table 1 Crovalimab Silo Data Collection Schedule

Data	Baseline (Enrollment Visit) ^a	Follow-up ^b	Participant Discontinuation of Crovalimab/Registr y Completion ^c
Crovalimab exposure (including dates and doses)	X	X	
Participant characteristics, demographics, clinical history, potential confounding factors, any ongoing safety events and concomitant medication	X		
Last PNH treatment (including date and dose, except for previous silo drug)	X		
Proportion of PNH cells (as measured by flow cytometry of granulocytes, monocytes, and erythrocytes)	X	X	X
AESIs, AEs, SAEs (including dates) ^d	X	X	X
Clinical events and outcomes ^e	X	X	X
Clinical laboratory test results related to PNH ^f	X	X	X
Obstetric history ^g	X		
Pregnancy status, outcome and maternal complications	X	X	X
AEs, adverse fetal/neonatal/infant outcomes and baby complications, including growth and development deficiency ^h		X	X
Breastfeeding information	X	X	X
Vaccination	X	X	X
Fatigue questionnaire ⁱ	X	X	

Data	Baseline (Enrollment Visit) ^a	Follow-up ^b	Participant Discontinuation of Crovalimab/Registr y Completion ^c
------	---	------------------------	--

AE = adverse event; ASEI = adverse event of special interest; FACIT = Functional Assessment of Chronic Illness Therapy; LDH = lactate dehydrogenase; MAVE = major adverse vascular event; PNH = paroxysmal nocturnal hemoglobinuria; SAE = serious adverse event; ULN = upper limit of normal.

- ^a Data from baseline will include information collected in the core and at the enrollment visit.
- ^b Data are expected to be entered in the electronic data capture system approximately every 6 months post-enrollment. Every participant will be followed up during their entire crovalimab treatment and up to 12 months after discontinuation of crovalimab, if they do not start a new complement inhibitor (or 12 weeks if they start a new complement inhibitor).
- ^c After discontinuation from crovalimab, participants with PNH would be followed up for 12 months from the discontinuation date of crovalimab (if they do not start a new complement inhibitor) or up to 12 weeks after discontinuation (if they start a new complement inhibitor).
- ^d Including serious infections, Meningococcal infection, development or worsening of any neurological condition (e.g., axonal neuropathy, multifocal mononeuropathy, etc.), malignancies and hematologic abnormalities, serious hemolysis in participants with PNH who discontinue crovalimab, transient immune complex reactions, and infusion and injection related reactions. Treatment, hospitalizations, outcomes and causality for AESIs, AEs, and SAEs will be also collected.
- ^e Including, but not limited to MAVEs (including thrombosis), packed red blood cell transfusions, breakthrough hemolysis, high disease activity status (evidence of $LDH \geq 1.5 \times ULN$ with any of the following symptoms: fatigue, hemoglobinuria, abdominal pain, shortness of breath, anemia (hemoglobin < 100 g/L), dysphagia, erectile dysfunction, development or worsening of autoimmune disease, bone marrow pathology and hematological disorders, impaired renal function, impaired hepatic function, and death.
- ^f Including, but not limited to hemoglobin, absolute reticulocyte count, LDH, $LDH \times ULN$, LDH ratio, haptoglobin, indirect and total bilirubin, AST/ALT, direct antiglobulin test.
- ^g Obstetric history (females): pregnancies, live births, miscarriages, and stillbirths, pregnancy or delivery complications, etc.
- ^h Serious safety events, baby complications, and postnatal growth of the infant through at least their first year of age. When possible, information will be categorized by intervals of 3, 6, 9, and 12 months of infant age.
- ⁱ Patient-reported fatigue assessment using the FACIT-Fatigue questionnaire.

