8.2 OBJECTIVES

The primary objectives for this study are as follows:

- To characterize and estimate the frequency of AESIs among participants with PNH exposed to crovalimab. AESIs are as follows:
 - Serious infections

- Meningococcal infection and other infections with encapsulated bacteria
- Development or worsening of any neurological condition (e.g., axonal neuropathy, multifocal mononeuropathy)
- Malignancies and hematologic abnormalities
- Serious hemolysis
- Transient immune complex reactions
- Infusion and injection-related reactions
- To characterize and estimate the frequency of AEs, SAEs, pregnancy outcomes, and infant outcomes in participants with PNH exposed to crovalimab during pregnancy and through breastfeeding. Specifically:
 - To estimate the frequency and further characterize all AEs, adverse pregnancy outcomes, and birth outcomes (during pregnancy until date of delivery), in pregnant female participants with PNH
 - To estimate the frequency and further characterize adverse fetal/neonatal/infant outcomes (e.g., major and minor congenital malformations, gestational age, postnatal growth and development) and SAEs at birth and through at least the first year of life of infants of mothers exposed to crovalimab during pregnancy
 - To estimate the frequency and further characterize all AEs for lactating females and infants exposed to crovalimab through breastfeeding

The secondary objectives for this study are as follows:

- To estimate the frequency and further characterize AEs and SAEs (not included as AESIs) in all participants with PNH exposed to crovalimab.
- To characterize clinical outcomes and laboratory test results relevant to PNH disease among participants with PNH who experienced an AESI
- To characterize patient-reported outcomes (PROs) among participants with PNH who experienced an AESI via a patient-reported fatigue assessment using the Functional Assessment of Chronic Illness Therapy (FACIT)-Fatigue questionnaire

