9.3.1.2.4 Malignancies and Hematologic Abnormalities

The presence and type of malignancy, onset and resolution date will be described.

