- Results in **persistent or significant disability/incapacity**: An event/reaction that results in a condition that substantially interferes with the activities of daily living of a study patient. Disability is not intended to include experiences of relatively minor medical significance such as headache, nausea, vomiting, diarrhea, influenza, and accidental trauma (e.g., sprained ankle).
- Is a **medically important event or reaction**: An important medical event/reaction that may not be immediately life-threatening or result in death or hospitalization, but based on medical judgment may jeopardize the patient and may require medical or surgical intervention to prevent any of the outcomes listed above (i.e., death of patient, life-threatening, hospitalization, prolongation of hospitalization, congenital anomaly/birth defect, or persistent or significant disability/incapacity). Examples of such events include allergic bronchospasm requiring intensive treatment in an emergency room or at home, blood dyscrasias or convulsions that do not result in inpatient hospitalization, or the development of drug dependency or drug abuse.
- Any suspected transmission via a medicinal product of an infectious agent is also considered as a SAE.

All AESIs, AEs, and SAEs will be recorded, including their corresponding dates and characteristics such as outcome, treatment, hospitalization, severity, seriousness, and de-/rechallenge.

9.3.1.3.2 Clinical Outcomes and Laboratory Test Results Relevant to PNH Among Participants who Experienced an AESI

The following clinical outcomes and laboratory test results related to PNH will be recorded among participants with PNH who experience an AESI:

- Major adverse vascular events (MAVEs), including thrombosis
 - If yes, type of event
- Red blood cell transfusions
 - Yes/No
 - Number of units received
- Breakthrough hemolysis (BTH)
 - Physician-defined BTH
 - Protocol-defined BTH
 - ≥ 1 new or worsening sign or symptom of intravascular hemolysis (fatigue, hemoglobinuria, abdominal pain, dyspnea, anemia [hemoglobin < 100 g/L], MAVE [including thrombosis], dysphagia, or erectile dysfunction) and elevated LDH ($\geq 2 \times$ the upper limit of normal [ULN]) after prior LDH reduction to $< 1.5 \times$ ULN on therapy
- High disease activity (HDA) status

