 - Evidence of intravascular hemolysis (LDH $\geq 1.5 \times$ ULN) and any of the following symptoms: fatigue, hemoglobinuria, abdominal pain, shortness of breath (dyspnea), anemia (hemoglobin < 100 g/L), MAVE (including thrombosis), dysphagia, or erectile dysfunction
- Development or worsening of autoimmune disease
 - If yes, type of event
- Bone marrow pathology
 - If yes, type of bone marrow pathology or other hematological disorder, % hemoglobin, absolute reticulocyte count, LDH, LDH \times ULN, LDH ratio, haptoglobin, indirect and total bilirubin, AST/ALT, direct antiglobulin test

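### The protocol contradicts itself on the scope of its primary AESIs: Table 1 footnote d limits serious hemolysis to participants who discontinue, and section 9.3.1.2.4 leaves hematologic abnormalities undescribed

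*Protocol*

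**What the plan says.** Section 8.2 names seven AESIs whose frequency is the first primary objective. Three matter here: "Serious hemolysis" with no condition on treatment status, "Malignancies and hematologic abnormalities", and "Meningococcal infection and other infections with encapsulated bacteria".

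Section 9.3.1.2 then describes each AESI. Section 9.3.1.2.5 describes serious hemolysis without limiting it to people who stop treatment, and section 9.3.1.2.2 keeps the other encapsulated bacteria. Section 9.3.1.2.4 has both halves in its heading, but its only sentence is: "The presence and type of malignancy, onset and resolution date will be described".

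Section 9.3.3 says data are collected according to Table 1. Footnote d to the AESI/AE/SAE row keeps both halves of the malignancy AESI, but lists hemolysis as "serious hemolysis in participants with PNH who discontinue crovalimab". For the encapsulated-bacteria AESI it names meningococcal infection alone.

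Section 9.7.1 counts each participant's first event and divides by the pooled person-time of the whole cohort. For AESIs that time starts at silo enrollment (section 9.2).

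**The concern.** Each AESI frequency is a primary result, so its case definition should be the same wherever it is stated. For serious hemolysis the objective and the variable definition cover everyone, while the collection schedule covers only those who discontinue. Someone working from Table 1 and someone working from section 9.3.1.2.5 would count different cases.

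The narrow version probably echoes the regulators' request in section 7, which concerns hemolysis after discontinuation. The objective is wider than that request.

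AESI status also decides who enters other analyses. Clinical and laboratory outcomes (section 9.3.1.3.2) and the fatigue questionnaire (section 9.3.1.4) are characterized in participants with an AESI. A hemolysis episode filed as an ordinary SAE would drop out of those as well, unless the participant had another AESI.

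**Working it through.** **Step 1: compare the three places.**

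| AESI | 8.2 | 9.3.1.2 | Table 1 footnote d |
|---|---|---|---|
| Serious hemolysis | all participants | all participants | only those who discontinue |
| Malignancy / hematologic abnormality | both | malignancy only | both |
| Encapsulated bacteria | meningococcal and others | meningococcal and others | meningococcal only |

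The other four AESIs (serious infections, neurological conditions, TICR, infusion and injection reactions) show no such narrowing. Each of the three narrowings occurs in one place only.

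**Step 2: effect on the hemolysis rate.** Let C be first episodes in participants who stay on treatment, D first episodes in those who discontinue, and T the pooled person-years.

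- Objective and definition: rate = (C + D) / T.
- Footnote d: rate = D / T′. T′ is at least T, because a participant whose episode is not counted goes on accruing time at risk.
- The footnote rate is therefore at most D / (C + D) of the intended rate. It is zero if every episode occurs in participants who stay on treatment.

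The documents give neither C nor D. Section 9.5 reports no serious hemolysis in the crovalimab trials, so a single reclassified case could decide whether the reported frequency is zero.

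**Step 3: reproduce Table 2.** With 300 participants, P(at least one event) = 1 − (1 − p)^300. This gives 77.8% at p = 0.5% and 95.1% at p = 1.0%, as printed. Table 2 thus assumes that all 300 can contribute a case.

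**Step 4: the same formula when only discontinuers can count.** The discontinuation shares are assumptions, and the prevalence is taken as equal in discontinuers and others. The last column is the exact upper 95% limit with zero events, 1 − 0.025^(1/n).

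| Share discontinuing | n | p = 0.5% | p = 1.0% | Upper limit, 0 events |
|---|---|---|---|---|
| all can count | 300 | 77.8% | 95.1% | 1.2% |
| 10% | 30 | 14.0% | 26.0% | 11.6% |
| 20% | 60 | 26.0% | 45.3% | 6.0% |
| 30% | 90 | 36.3% | 59.5% | 4.0% |
| 50% | 150 | 52.9% | 77.9% | 2.4% |

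At 20% discontinuing and p = 1.0%, the expected cases are 300 × 0.01 = 3 under the objective and 60 × 0.01 = 0.6 under the footnote. Divided by all 300, the footnote count gives 0.6 / 300 = 0.2% instead of 1.0%. A result of zero over 300 would carry an upper limit of 1.2%, although only 60 people could have contributed a case (6.0%).

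**Step 5: hematologic abnormalities.** Footnote d keeps them in the AESI, but section 9.3.1.2.4 does not say what will be described. The nearest variable is in section 9.3.1.3.2 ("If yes, type of bone marrow pathology or other hematological disorder"). It is secondary and, by that section, "will be recorded among participants with PNH who experience an AESI". Table 1 footnote e schedules bone marrow pathology and hematological disorders without that condition. The protocol does not say whether this item is the source for the AESI.

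**Step 6: encapsulated bacteria.** A serious infection with another encapsulated organism still counts under the serious-infections AESI. Only the sub-category count and non-serious cases depend on the footnote.

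**The case against.** The strongest reply is that nothing is lost at collection. Footnote d hangs on a row that covers all AESIs, AEs and SAEs, it opens with an inclusive word, and section 9.3.1.3.1 says all of them will be recorded. This is also a secondary-data study: sites follow the silo registry's own protocol and eCRF, which are not shown, and the SAP could restate the case definitions.

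Much of that stands. The events are recorded, so what is at risk is their classification. How sites will classify them cannot be known from this document. The reply does not remove the contradiction, however. Footnote d lists seven items that match the seven AESIs one for one. Footnotes e and f state that their lists are not exhaustive and footnote d does not, so it reads as the AESI list. A later SAP can choose a definition, but it may not recover an AESI label that was never assigned when the event was entered.

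Three stronger readings are tempting, and the documents do not support them.

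- A reader might infer that isolated marrow failure falls outside both the primary and the secondary results. Footnote d still names hematologic abnormalities as an AESI, and any new disease is at least an AE under section 9.3.1.3.1.
- A reader might infer that on-treatment and post-discontinuation hemolysis cannot be distinguished. Event onset dates and crovalimab exposure dates are both collected, so they can be; the protocol just does not plan to report them apart.
- A reader might size the loss as the share of follow-up spent on treatment. The footnote restricts by participant, not by time, and the protocol gives no treatment duration.

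**Conclusion.** The point holds as an internal contradiction, mainly for serious hemolysis: one primary AESI has two incompatible scopes, and the narrower one lowers a rate whose denominator still includes everyone. The hematologic half of another AESI has no description in its own section. The omission of other encapsulated bacteria is minor.

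The consequence is cases moving from primary to secondary tables. The size depends on how many participants discontinue and where the hemolysis falls, and the protocol states neither. The figures of 14.0% to 52.9% against 77.8% (at 0.5% prevalence) rest on assumed discontinuation shares of 10% to 50% and equal risk in both groups. If hemolysis clusters after stopping, as section 7 fears, the footnote would lose a smaller share of cases. Table 2 itself is correct for 300 participants and is not in dispute.

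**What to change.** - **Footnote d:** reconcile it with sections 8.2, 9.3.1.2.2 and 9.3.1.2.5 by removing the discontinuation restriction on serious hemolysis and adding the other encapsulated bacteria.
- **Section 9.3.1.2.4:** extend it to report hematologic abnormalities in all participants, separately from malignancy. The sponsor should state whether the bone marrow pathology and hematological disorder item in footnote e is the source.
- **Reporting:** present serious hemolysis on treatment and after discontinuation separately, from the event and exposure dates already collected. This answers the regulators' narrower question without narrowing the objective.

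The cost is protocol wording and any matching eCRF wording. The sponsor approves the eCRF specifications (section 9.6), and no new assessment is needed. AESI counts may become slightly higher.

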9.4 DATA SOURCE

This study will analyze individual patient-level data collected from the Crovalimab Silo registry. A description of the Crovalimab Silo can be found in Section 9.1.

9.5 STUDY SIZE

Enrollment will depend on the approval timelines, uptake and treatment course in each country where the sites are open, as well as the total number of evaluable participants with PNH for AESIs (described in Section 9.3.1.2). However, based on patient projections in selected countries, the MAH expects 300 participants with PNH to be enrolled with up to 7 years of follow-up during the duration of the Crovalimab Silo registry (7 years).

[Table 2](#) provides probabilities (and associated 2-sided 95% CIs) to observe at least one event for AESIs with assumed prevalence ranging from 0.5%–20% in a population of 300 participants with PNH. For example, in the crovalimab trials, 6% of patients had a serious infection, 6.4% had an injection-related reaction, and 17.8% had a TICR, while no patients presented with a meningococcal infection or a serious hemolysis (Crovalimab E.U. Risk Management Plan [RMP] Version 1.0, 28 June 2024).

Table 2 Probability to Observe at least one Event for AESIs with Varying Prevalence

Assumed Prevalence ^a	Probability to Observe at least One AESI (95% CI)
0.5%	77.8% (10.2%–99.8%)
1.0%	95.1% (46.2%–100.0%)
1.5%	98.9% (74.3%–100.0%)
2.0%	99.8% (89.1%–100.0%)
5.0%	100.0% (100.0%–100.0%)
7.0%	100.0% (100.0%–100.0%)
10.0%	100.0% (100.0%–100.0%)
15.0%	100.0% (100.0%–100.0%)
20.0%	100.0% (100.0%–100.0%)

AESI = adverse event of special interest.

Note: 95% CIs are 2-sided and were calculated using Clopper-Pearson method (Clopper and Pearson 1934).

^a Assumed prevalence obtained during whole follow-up period.

In addition, the MAH aims to enroll approximately 25 participants with PNH who are pregnant in the Crovalimab Silo registry. Nevertheless, since the management of PNH during pregnancy has been challenging and pregnancy has been discouraged in participants with PNH, there are very few reported cases of pregnant participants with PNH treated with C5 inhibitors. For example, in a similar registry, there were only 94 pregnancies in fewer than 1,086 females treated with eculizumab from June 2006 to November 2014 (Kelly et al. 2015; Höchsmann et al. 2022).

In real-world clinical practice, treatment switching is common for various personal or medical reasons. Furthermore, the potential for loss to follow-up (including death, registry participation or consent withdrawal) and variations in the standard of care (SOC) across different countries can also preclude the possibility of maintaining a minimum 5 –year follow-up for all participants with PNH.

The MAH will proactively consider renegotiation with the IPG registry if required to extend the Crovalimab Silo primary data collection study duration, depending on enrollment of pregnant participants with PNH and participant follow up. Consistent with the commitment to obtaining pregnancy safety data, participant recruitment and follow-

up progress will be closely monitored, and updates will be provided as part of interim reports. In parallel, the MAH will investigate alternative approaches for data collection to supplement enrollment, if needed.

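### Table 2 puts 95% confidence intervals around detection probabilities that are fixed by the assumed prevalence, and so does not show the precision the estimation objective needs

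*Protocol*

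**What the plan says.** Section 9.5 takes the cohort size from enrolment projections: "the MAH expects 300 participants with PNH to be enrolled with up to 7 years of follow-up". Its only statistical support is Table 2, described as a table that "provides probabilities (and associated 2-sided 95% CIs) to observe at least one event for AESIs with assumed prevalence". The table covers nine prevalence values in 300 participants, and a footnote to the prevalence column reads "Assumed prevalence obtained during whole follow-up period". The note on method says "95% CIs are 2-sided and were calculated using Clopper-Pearson method".

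The printed entries are 77.8% (10.2% to 99.8%) at 0.5%, 95.1% (46.2% to 100.0%) at 1.0%, 98.9% (74.3% to 100.0%) at 1.5% and 99.8% (89.1% to 100.0%) at 2.0%. All five rows from 5% to 20% read 100.0% (100.0% to 100.0%).

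The same section cites trial frequencies of 6% for serious infection, 6.4% for injection-related reaction and 17.8% for TICR, and no meningococcal infection or serious hemolysis. Section 8.2 makes estimation of AESI frequency a primary objective. Section 9.7.1 plans exact 95% intervals and no formal testing.

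**The concern.** A confidence interval describes the uncertainty of something estimated from data. Here the prevalence is an assumption and the number of participants is given, so the detection probability is a calculated constant. Printing 10.2% to 99.8% beside 77.8% tells a regulator that the chance of detecting a 0.5% event is almost unknown. Under the stated assumptions it is 77.8%.

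The second issue is fit to purpose. A study that sets out to estimate frequencies is judged by the width of its intervals and, for events not yet seen, by the upper limit when none occur. Table 2 shows neither on the frequency scale. At 5% and above, where the cited non-zero AESI frequencies lie, its entries no longer vary.

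**Working it through.** **Inputs (Section 9.5).** n = 300; assumed prevalence p as listed in Table 2; two-sided 95% Clopper-Pearson limits.

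**Step 1: point values.** P(at least one event) = 1 − (1 − p)^300.

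- p = 0.5%: 1 − 0.995^300 = 77.77%, printed 77.8%
- p = 1.0%: 1 − 0.99^300 = 95.10%, printed 95.1%
- p = 1.5%: 1 − 0.985^300 = 98.93%, printed 98.9%
- p = 2.0%: 1 − 0.98^300 = 99.77%, printed 99.8%
- p = 5% and above: rounds to 100.0%, as printed

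All nine printed probabilities are correct.

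**Step 2: where the intervals come from.** Set x = 300p as if it were an observed count. Take L = the 0.025 quantile of Beta(x, 301 − x) and U = the 0.975 quantile of Beta(x + 1, 300 − x). Then transform each limit to 1 − (1 − L)^300 and 1 − (1 − U)^300.

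| p | x | Limits for p | Transformed limits | Printed |
|---|---|---|---|---|
| 0.5% | 1.5 | 0.036% to 2.121% | 10.24% to 99.84% | 10.2% to 99.8% |
| 1.0% | 3 | 0.207% to 2.894% | 46.25% to 99.99% | 46.2% to 100.0% |
| 1.5% | 4.5 | 0.452% to 3.614% | 74.29% to 100.0% | 74.3% to 100.0% |
| 2.0% | 6 | 0.737% to 4.302% | 89.14% to 100.0% | 89.1% to 100.0% |
| 5.0% | 15 | 2.825% to 8.113% | 99.98% to 100.0% | 100.0% to 100.0% |

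This construction reproduces the printed intervals. Two alternatives do not:

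- Rounding 1.5 to 1 or 2 events gives lower limits of 2.5% or 21.5% in the first row.
- Applying Clopper-Pearson directly to the probability, with n = 300, gives 72.6% to 82.3% in that row.

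The table therefore treats the assumed prevalence as if it had been estimated from the future 300 participants. In two rows it does so with event counts that cannot occur.

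**Step 3: what 300 participants would deliver.** Exact 95% interval of the incidence proportion, assuming all 300 are evaluable:

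| Assumed incidence | Events | Exact 95% interval |
|---|---|---|
| none seen | 0 | 0% to 1.2% |
| 1% | 3 | 0.2% to 2.9% |
| 2% | 6 | 0.7% to 4.3% |
| 5% | 15 | 2.8% to 8.1% |
| 6% | 18 | 3.6% to 9.3% |
| 6.4% | 19 (19.2 rounded) | 3.9% to 9.7% |
| 7% | 21 | 4.4% to 10.5% |
| 10% | 30 | 6.8% to 14.0% |
| 15% | 45 | 11.2% to 19.6% |
| 20% | 60 | 15.6% to 25.0% |

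The zero-event limit is 1 − 0.025^(1/300) = 1.22%. The 0.5% and 1.5% rows fall between whole counts, so neighbouring counts serve: 1 event gives 0.01% to 1.8% and 2 events 0.1% to 2.4%; 4 events give 0.4% to 3.4% and 5 events 0.5% to 3.8%.

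For the separate target of about 25 pregnancies, the zero-event limit is 1 − 0.025^(1/25) = 13.7%, and one event gives 0.1% to 20.4%.

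**The case against.** The best defence is that nothing in Table 2 is miscalculated. Every probability is right, and the limits follow from the method the note names. They are also not empty: for 0.5% to 2% they are transformed exact limits for the prevalence, and the 1% row converts back to the 0.2% to 2.9% shown above. That stands. The fault is an invalid interval and its label, not an arithmetic slip, and it would go too far to call the intervals meaningless. But nobody can read the precision off that scale, and from 5% upward it is lost altogether.

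It is also true that the 300 comes from enrolment projections, that no test or decision rule uses the table, and that the chance of at least one event is a reasonable measure for AESIs with no trial cases. These points limit the consequence. They do not justify the intervals.

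Three stronger readings are tempting, and the protocol does not support them:

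- **The denominator of 300 is wrong for pregnancy.** Table 2 covers AESIs only. Pregnancy has its own paragraph and its own target of about 25.
- **The table assumes that all 300 complete follow-up.** The footnote says only that the prevalence is the one obtained over the whole of follow-up, which may already reflect attrition. The text after the table says that switching and losses may prevent a five-year minimum.
- **The TICR entry fails because only switchers are at risk.** Section 7 does tie TICR to switching, but the protocol gives neither the number of switchers expected nor the denominator behind 17.8%. No alternative denominator can be sourced, and for the same reason no interval for TICR at n = 300 is offered here.

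**Conclusion.** The point holds in this form. The 95% intervals in Table 2 are not valid confidence intervals for the stated probabilities, which are fixed once p and n are given. The four rows from 0.5% to 2% should read 77.8%, 95.1%, 98.9% and 99.8% with no interval. The table also gives no usable precision for AESIs at the cited frequencies of 6%, 6.4% and 17.8%, although estimating those frequencies is the objective.

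The intervals in Step 3 rest on all 300 being evaluable for the event; with fewer, they widen. The consequence is moderate: the only statistical support for the study size misleads its reader, but neither the planned analyses nor the conduct of the study depends on it.

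**What to change.** In Table 2, delete the intervals from the probability column and the note on how they were calculated. Add a column with the expected exact 95% interval of the incidence proportion at each assumed value for n = 300, plus a zero-event row with its upper limit of 1.2%. Use whole event counts, and state that the figures assume all 300 are evaluable. Rows at 6% and 6.4% would tie the table to the trial frequencies quoted above it.

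Optionally, give the same for about 25 pregnancies (no events: upper limit 13.7%).

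The cost is one replaced table and a sentence of text. Study size, data collection and planned analyses stay as they are.
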